### **10.3. Deaths, Serious Adverse Events, and Other Significant Adverse Events**

Deaths and other serious or significant adverse events will be encompassed by the various adverse event types defined in Section 10.2, and these events will be summarized and listed as described in that section.

A separate listing will be created for all deaths summarizing the time to death and cause of death.

### **10.4. Clinical Laboratory Evaluation**

Virus serology for human immunodeficiency virus, HBsAg, and anti-HCV antibody collection date and results at screening will be listed for all participants.

Clinical chemistry (including liver function), hematology, and thyroid-stimulating hormone laboratory results at screening will be listed, as well as all results that may be collected for early termination or unscheduled visits.

### **10.5. Vital Signs, Physical Findings, and Other Observations Related to Safety**

#### **10.5.1. Vital Signs**

Vital signs parameters of blood pressure (systolic and diastolic; mmHg), heart rate (beats/minute), respiratory rate (breaths/minute), oral temperature (°F), and weight (kg) will be

summarized for Screening, and pre-dose for Visit 1 and Visit 2 by dosing sequence. For all results collected post-baseline, change from baseline will be displayed. Visit 1 pre-dose vital signs results will be considered baseline for summaries of vital signs data. If the Visit 1 pre-dose result is missing, screening results will be considered baseline.

Separately, blood pressure and heart rate will be collected every 15 minutes for the first hour post-dose, every 20 minutes for the second hour post-dose, and every 30 minutes for the third and fourth hour post-dose. These results will be summarized by dose received. Change from baseline will be summarized, with baseline being defined as the pre-dose value for the applicable dose received.

All vital signs will be listed in by- participant listings including visit and collection date.

### **10.5.2. Physical Examinations**

A physical examination will be performed at the Screening Visit to assess and confirm eligibility. The examination will include a general assessment of the skin, head, ears, eyes, nose, throat, neck, oral cavity, thyroid, lungs, heart, abdomen, lymph nodes, and musculoskeletal system/extremities, and a neurological examination. A symptom-based physical examination may be performed at dosing visits, or at an Unscheduled or ET Visit per the investigator's discretion.

In general, clinically significant abnormal findings are expected to be associated with an item recorded in the participant's medical history (when detected at Screening) or as an AE (when detected after Screening). Physical exam results will not be reported otherwise.

### **10.5.3. Other Safety Measures**

#### **10.5.3.1 Electrocardiogram**

A standard 12-lead electrocardiogram (ECG) will be recorded and assessed at the Screening Visit, Visit 1 (pre-dose), and Visit 2 (pre-dose). Additionally, an ECG may be performed for any complaints of chest discomfort, lightheadedness, and/or palpitations per the investigator's discretion and repeated as needed during Visit 1 (post-dose) and Visit 2 (post-dose). ECGs may also be performed at an Unscheduled or ET Visit per the investigator's discretion. Results will be reported in data listings, including visit and collection date.

#### **10.5.3.2 Pregnancy Assessments**

Pregnancy assessments will be done at Screening and pre-dose Visit 1 and Visit 2. Date, time, and results of each pregnancy assessment will be listed for all female participants. In the case of one or more pregnancies occurring during study participation, a data listing will be prepared to display applicable information, including date reported, method of pregnancy confirmation, delivery date (if applicable), pregnancy termination status and week (if applicable), and any problems or congenital abnormalities present for each birth.

## 11. PHARMACOKINETIC EVALUATION

All pharmacokinetic (PK) analyses will be performed on the PK analysis population and the per protocol population (if the per protocol population differs from the PK analysis population).

The primary analyses will be performed on the PK analysis population. All PK analyses performed on the per protocol population will be considered supportive analyses.

Subject time-concentration data without evaluable results will be excluded from analyses on the PK analysis population separately for each PK parameter.

Actual PK sample collection times will be used in analyses. If a collection time is incomplete or missing, the nominal time will be used for analyses.

Atropine concentrations marked as “not detectable” will be imputed as half of the lower limit of quantitation in analyses.

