## 2. PURPOSE OF THE ANALYSES

The purpose of this Statistical Analysis Plan (SAP) is to describe the planned analyses and data displays to be included in the Clinical Study Report (CSR) for Protocol BP-C-24-001/SABER. This document provides details on study populations, how the variables will be derived, how missing data will be handled and details on statistical methods to be used to analyze the safety and pharmacokinetic data.

The SAP is based on International Council for Harmonisation (ICH) guidelines E3, E9 (Statistical Principles for Clinical Trials), and E9 (R1).

The document may evolve over time, for example, to reflect the requirements of protocol amendments or regulatory requests. However, the final SAP must be finalized, approved by Biomedical Advanced Research and Development Authority (BARDA), and placed on file before database is locked and pharmacokinetic analysis occurs. If differences occur between analyses described in the SAP and the current protocol, those found in this SAP will assume primacy. Deviations from the final approved plan will be noted in the CSR. Table, figure, and listing specifications are provided in separate documents.

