Volunteers will be screened for study participation from Days -14 to -3. After Screening on Day 1, eligible participants will be enrolled and will be randomized to receive one of two dosing sequences as presented in the table above. Once randomized, each participant will receive 2 doses of atropine separated by a wash out period of  $6 \pm 1$  days. During Visit 1 (Day 1) and Visit 2 (Day 8), participants will be administered SL or IM atropine, according to their randomly assigned dosing sequence. At each dosing visit, blood samples for PK will be collected at time 0 (pre-dose) and at 13 time points post-dose at 5, 10, 15, 20, 30, 45, 60, and 90 minutes and 2, 2.5, 4, 6, and 8 hours after dosing. Participants will be discharged from the clinic after the 8-hour blood sample collection. Participants will be followed for approximately 6 days after their last dose.

**Number of participants (planned):** Approximately 46 enrolled for 36 evaluable

**Diagnosis and main criteria for inclusion:** Healthy male and non-pregnant female participants aged 18 through 65 years, inclusive.

Eligibility criteria will be assessed at Screening and must be reviewed just prior to each dose of atropine. Criteria specified as only being evaluated at Screening or at Pre-dose Visits will be assessed only at those visits. If the participant no longer meets applicable eligibility criteria, the investigator, in consultation with the medical monitor in cases of uncertainty, must determine whether the participant should receive the atropine dose or be terminated early from study drug.

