### 11.1. Pharmacokinetic Endpoints

The following PK parameters contribute to the analysis of the primary endpoint for this study:

- Area under the analyte concentration versus time curve to infinity ( $AUC_{\infty}$ )
- Area under the analyte concentration versus time curve to time of last quantifiable data point ( $AUC_t$ )

Additionally, the following PK parameters contribute to the analysis of the secondary endpoints for this study:

- Area under the analyte concentration versus time curve to 45, 60, 90, 120, 150, and 240 minutes ( $AUC_{45}$ ,  $AUC_{60}$ ,  $AUC_{90}$ ,  $AUC_{120}$ ,  $AUC_{150}$ , and  $AUC_{240}$ , respectively)
- Maximum measured plasma concentration ( $C_{max}$ )
- Time to  $C_{max}$  ( $t_{max}$ )
- Apparent terminal elimination half-life ( $t_{1/2}$ )
- Terminal elimination rate constant ( $\lambda_z$ )
- Volume of distribution ( $V_d/F$ )
- Total body clearance ( $CL/F$ )
- Absorption rate constant ( $K_a$ )

Additional PK parameters may be resulted for exploratory purposes.

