## 11.2. Pharmacokinetic Methods

### 11.2.1. Pharmacokinetic Endpoint Estimation

Phoenix WinNonLin software Version 8.3 or later will be used to generate PK parameter estimates.

The PK parameters will be estimated for each subject and route of administration using the noncompartmental method for extravascular dosing routes, using the linear log trapezoidal rule and uniform weighting for plasma models.

The terminal elimination rate constant ( $\lambda_z$ ) will be calculated using the best fit method. Parameters  $AUC_{\infty}$ ,  $t_{1/2}$ ,  $CL/F$  and  $V_d/F$  will be non-evaluatable when there are fewer than 3 data points beyond  $t_{max}$  in the time-concentration curve.

The absorption rate constant ( $K_a$ ) for each route of administration will be computed as a slope over a user-defined range after review of subject specific time-concentration profiles. Rate constants may also be calculated using the best-fit method for linear regression in addition to user-defined ranges.

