### 11.2.2. Statistical Analysis of Pharmacokinetic Endpoints

PK parameters will be summarized by route of administration using descriptive statistics on the scales outlined below.

For the PK parameters  $AUC_{\infty}$ ,  $AUC_t$ ,  $AUC_{45}$ ,  $AUC_{60}$ ,  $AUC_{90}$ ,  $AUC_{120}$ ,  $AUC_{150}$ , and  $AUC_{240}$ , and  $C_{max}$ , the following will be displayed in the summary table:

- a. Count of subjects with non-missing data for the applicable analysis
- b. Geometric mean
- c. CV% of the geometric mean, which is calculated using the following equation:  
$$\sqrt{10^{\ln(10) \times (SD(\log_{10} value))^2}} - 1 \times 100$$
- d. Minimum and maximum values
- e. Median, and 1st and 3rd quartile values

For the PK parameters  $t_{max}$ ,  $t_{1/2}$ ,  $\lambda_z$ ,  $CL/F$ ,  $V_d/F$ , and  $K_a$  the following descriptive summary statistics will be reported on the untransformed scale:

- a. Count of subjects with non-missing data for the applicable analysis
- b. Arithmetic mean
- c. Standard deviation
- d. Minimum and maximum values
- e. Median, and 1st and 3rd quartile values

Bioavailability of SL administration of atropine sulfate relative to that of IM atropine sulfate will be assessed based on ratios of least-square means and their associated 90% confidence intervals (CIs) generated from linear mixed models to the log-transformed PK parameters including terms for dosing sequence, route (SL or IM), and period as fixed effects, and subject nested within dosing sequence as a random effect. No adjustment will be made for dosing cohort or the interaction for dosing cohort and route.

Ratios of least-squares means of key plasma PK parameters and associated 90% CIs from the linear mixed model will be anti-log transformed to obtain estimates on the original scale.

Bioequivalence will be considered met if the 90% CI of the ratio for  $AUC_{\infty}$  and  $AUC_t$  lie within 80.00 to 125.00%.

Subject specific and population time-concentration profiles on both log and linear scales will be presented. Additionally, PK parameters will be listed by route of administration and subject.

As a supportive analysis of bioavailability, descriptive summary statistics will be displayed in tables for subject-specific ratios between routes of administration.

For each PK parameter, boxplots will be displayed for each route of administration with subject specific lines overlaid.

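### SAP 11 sets not-detectable concentrations to half the LLOQ at any position, so imputed tail values can enter λz and the extrapolation of AUC∞, a co-primary parameter

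*SAP*

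**What the plan says.** - **ND rule.** SAP section 11 states that ND atropine concentrations "will be imputed as half of the lower limit of quantitation in analyses". It does not separate pre-dose samples, samples between quantifiable values, and samples after the last quantifiable value. Neither document ties ND to the LLOQ, so a detectable value below the LLOQ has no rule.
- **λz.** SAP section 11.2.1 says that it "will be calculated using the best fit method". The regression points need not be quantifiable.
- **Evaluability.** AUC∞, t½, CL/F and Vd/F "will be non-evaluatable when there are fewer than 3 data points beyond" tmax. The count is of data points, not of quantifiable ones.
- **Exclusion.** Time-concentration data "without evaluable results will be excluded from analyses on the PK analysis population separately for each PK parameter" (SAP section 11). An imputed ND value is not described as non-evaluable.
- **AUCt.** SAP section 11.1 defines it as "Area under the analyte concentration versus time curve to time of last quantifiable data point". Neither document defines the last concentration used to extrapolate to infinity.
- **Decision rule.** SAP section 11.2.2: "Bioequivalence will be considered met if the 90% CI of the ratio for" AUC∞ and AUCt lies within 80.00 to 125.00%. Both must pass.

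**The concern.** AUC∞ is the area to the last concentration plus that concentration divided by λz. A placeholder in the tail acts on all three pieces: it extends the observed area, replaces the last concentration and changes the slope. If the true value is well above half the LLOQ, the placeholder pulls the tail down, steepens λz and shrinks AUC∞. If the true value is below half the LLOQ, or several tail samples share the same placeholder, the tail flattens and AUC∞ can grow. The error therefore changes sign between profiles, and it need not cancel between routes if one route reaches the limit sooner.

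AUCt and AUC∞ could also end at different times in the same profile. If the point is left open, it will be settled with concentrations in view in a study where no party is blinded (SAP section 8.2).

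**Working it through.** **1. The plan's own figure.** Inputs from Protocol section 13.2: SD of the log10 difference in AUC∞ 0.102, inflation factor 1.25, CV 0.212, N = 36, limits 0.80 to 1.25.

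- SD on the ln scale: 0.102 × ln 10 = 0.235; × 1.25 = 0.2936.
- Within-participant SD: 0.2936/√2 = 0.2076; CV = √(exp(0.2076²) − 1) = 0.210 (stated 0.212).
- With the stated CV: s = √ln(1 + 0.212²) = 0.2097; SE = 0.2097 × √(2/36) = 0.0494; 34 df.
- Exact power of two one-sided tests: 99.5% at ratio 1.0, 96.1% at 0.95, 96.5% at 1.05. This agrees with the stated >99% and 96%. These figures make no allowance for tail handling.

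**2. The three-point rule.** The late samples are at "2, 2.5, 4, 6, and 8 hours after dosing".

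| tmax | Scheduled samples after tmax | NDs needed to leave fewer than 3 quantifiable |
|---|---|---|
| 30 min | 8 | 6 |
| 1 h | 6 | 4 |
| 2 h | 4 | 2 |
| 2.5 h | 3 | 1 |

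With complete sampling, any tmax up to 2.5 h leaves 4, 6 and 8 h, which is three data points even if all three are imputed. Read literally, the rule fails only when tmax is 4 h or later. But imputation rescues a poor profile only when tmax is late or many samples are ND, which should be rare.

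**3. Effect on AUC∞.** From the documents: the sampling times, and the 1.0 mg SL geometric mean AUC∞ of 493.81 min·ng/mL (Protocol section 5.3), so 493.81/60 = 8.23 h·ng/mL. Assumed: half-life 2, 3 or 4 h; ka 4 per hour; LLOQ 0.1 to 0.75 ng/mL; ND means below LLOQ.

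- Profile: C(t) = AUC × k·ka/(ka − k) × (e^(−kt) − e^(−ka·t)), with k = ln 2/half-life and no noise.
- Estimation: linear-up/log-down trapezoids; λz by best adjusted R² on at least three points after tmax.
- AUC∞ = AUC to last + C_last × t½/ln 2.

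| Half-life | C at 4 h | C at 6 h | C at 8 h (ng/mL) |
|---|---|---|---|
| 2 h | 0.781 | 0.390 | 0.195 |
| 3 h | 0.801 | 0.505 | 0.318 |
| 4 h | 0.745 | 0.527 | 0.373 |

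Worked case, half-life 2 h and LLOQ 0.2: the 8 h value of 0.195 is replaced by 0.100.

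- Quantifiable points only: 7.08 + 0.390 × 2.00/0.693 = 8.21, which is 0.998 of true.
- Rule as written: 7.51 + 0.100 × 1.66/0.693 = 7.75, which is 0.942 of true. The half-life reads 1.66 h instead of 2.00 h.

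| Half-life | LLOQ | Tail NDs | Quantifiable only, AUC∞/true | As written, AUC∞/true |
|---|---|---|---|---|
| any | 0.1 | 0 | no effect | no effect |
| 2 h | 0.2 | 1 | 0.998 | 0.942 |
| 2 h | 0.3 | 1 | 0.998 | 0.971 |
| 2 h | 0.5 | 2 | 0.999 | 0.987 |
| 2 h | 0.75 | 2 | 0.999 | 1.117 |
| 3 h | 0.5 | 1 | 0.999 | 0.941 |
| 3 h | 0.75 | 2 | 0.995 | 1.004 |
| 4 h | 0.5 | 1 | 0.996 | 0.860 |
| 4 h | 0.75 | 3 | 1.000 | 0.845 |

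At half-lives of 3 and 4 h there is also no effect at LLOQ 0.2 and 0.3, because no tail value falls below the limit. The as-written runs also impute the pre-dose sample. Its added area is at most 0.375 × (5/60)/2 = 0.016 h·ng/mL, or 0.2% of 8.23, so the tail drives the result.

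**4. What ND means.** Suppose ND means below LLOQ/3. At LLOQ 0.5 the cut-off is 0.167, under the lowest 8 h value of 0.195, so nothing is imputed in the tail and the effect is nil for every LLOQ up to 0.5. At LLOQ 0.75 the cut-off is 0.25, and the 2 h half-life profile is caught again.

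**The case against.** **Size.** The documents give no LLOQ, half-life or ND frequency. An assay with an LLOQ near 0.1 ng/mL makes the point moot in these profiles, and so does a low detection limit at LLOQ up to 0.5. This stands. The percentages above are illustrations, not forecasts.

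**Power.** A reader might infer that the planned 96% power is lost. The documents do not support a figure. Protocol section 13.2 already multiplies the prior SD by 1.25, so if the prior value of 0.235 carried over, tail noise would have to raise it by more than 25% to exceed the planned 0.2936. That margin was set aside for unknown SL-to-IM variability, so it is not free to spend. It does mean that no expected power loss can be claimed.

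**False pass.** A reader might infer a risk of wrongly declaring bioequivalence. That is not shown: the distortion runs both ways, and AUCt must also pass.

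**AUCt.** A reader might think that it is corrupted as well. SAP section 11.1 ends it at the last quantifiable point, so it is not.

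**Last concentration.** It can be argued that the AUCt definition implies the same end point for AUC∞. That is a sensible reading, but it is written for AUCt alone and does not reach the λz regression. Nor does the ban on imputation in Protocol section 13.3.5 settle it: that concerns descriptive summaries, and SAP section 2 gives the SAP primacy.

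**The remedy is not always better.** When most tail samples are ND, quantifiable-only estimation extrapolates heavily. At half-life 4 h and LLOQ 0.75 the observed area is 2.55 of 8.23, so 69% is extrapolated. This stands, and it is why a sensitivity analysis is needed.

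**Conclusion.** Wrong as written, with low-to-moderate weight. The text allows placeholder values after the last quantifiable concentration to set λz and the last concentration, and so to distort AUC∞, t½, CL/F and Vd/F. In the illustration, single-profile AUC∞ runs from about -16% to +12% of true, against 0.995 to 1.000 of true with quantifiable points only. This rests on the assumed half-lives, absorption rate and LLOQs, on profiles scaled to the earlier SL result, and on reading ND as below LLOQ. The effect is zero when the 8 h samples are quantifiable. The λz and last-concentration route is the material one; the three-point rule is a minor part. The likely consequence is added variability in one of two parameters that must both pass, and so some loss of power for a truly equivalent product.

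**What to change.** In SAP section 11:

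1. Define 'not detectable' relative to the LLOQ, and say how detectable values below the LLOQ are handled. This comes first, because it largely decides whether the rule matters.
2. Add: 'Imputed values after the last quantifiable concentration are not used for λz, do not serve as the last concentration for extrapolation, and do not count toward the 3 data points beyond tmax.'
3. Prespecify a sensitivity analysis that reports AUC∞ with half-LLOQ tails.

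The cost is a few sentences and one more run of the same noncompartmental analysis. No new data, visits or participants are needed. SAP section 2 requires the plan to be final "before database is locked and pharmacokinetic analysis occurs", so the change belongs before that point. The downside is that some profiles may lose AUC∞, and AUC∞ may be more variable if the LLOQ is high enough that most tail samples are ND. The sensitivity run covers that case.

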### 11.1. Pharmacokinetic Endpoints

The following PK parameters contribute to the analysis of the primary endpoint for this study:

- Area under the analyte concentration versus time curve to infinity ( $AUC_{\infty}$ )
- Area under the analyte concentration versus time curve to time of last quantifiable data point ( $AUC_t$ )

Additionally, the following PK parameters contribute to the analysis of the secondary endpoints for this study:

- Area under the analyte concentration versus time curve to 45, 60, 90, 120, 150, and 240 minutes ( $AUC_{45}$ ,  $AUC_{60}$ ,  $AUC_{90}$ ,  $AUC_{120}$ ,  $AUC_{150}$ , and  $AUC_{240}$ , respectively)
- Maximum measured plasma concentration ( $C_{max}$ )
- Time to  $C_{max}$  ( $t_{max}$ )
- Apparent terminal elimination half-life ( $t_{1/2}$ )
- Terminal elimination rate constant ( $\lambda_z$ )
- Volume of distribution ( $V_d/F$ )
- Total body clearance ( $CL/F$ )
- Absorption rate constant ( $K_a$ )

Additional PK parameters may be resulted for exploratory purposes.

## 11.2. Pharmacokinetic Methods

### 11.2.1. Pharmacokinetic Endpoint Estimation

Phoenix WinNonLin software Version 8.3 or later will be used to generate PK parameter estimates.

The PK parameters will be estimated for each subject and route of administration using the noncompartmental method for extravascular dosing routes, using the linear log trapezoidal rule and uniform weighting for plasma models.

The terminal elimination rate constant ( $\lambda_z$ ) will be calculated using the best fit method. Parameters  $AUC_{\infty}$ ,  $t_{1/2}$ ,  $CL/F$  and  $V_d/F$  will be non-evaluatable when there are fewer than 3 data points beyond  $t_{max}$  in the time-concentration curve.

The absorption rate constant ( $K_a$ ) for each route of administration will be computed as a slope over a user-defined range after review of subject specific time-concentration profiles. Rate constants may also be calculated using the best-fit method for linear regression in addition to user-defined ranges.

### 11.2.2. Statistical Analysis of Pharmacokinetic Endpoints

PK parameters will be summarized by route of administration using descriptive statistics on the scales outlined below.

For the PK parameters  $AUC_{\infty}$ ,  $AUC_t$ ,  $AUC_{45}$ ,  $AUC_{60}$ ,  $AUC_{90}$ ,  $AUC_{120}$ ,  $AUC_{150}$ , and  $AUC_{240}$ , and  $C_{max}$ , the following will be displayed in the summary table:

- a. Count of subjects with non-missing data for the applicable analysis
- b. Geometric mean
- c. CV% of the geometric mean, which is calculated using the following equation:  
$$\sqrt{10^{\ln(10) \times (SD(\log_{10} value))^2}} - 1 \times 100$$
- d. Minimum and maximum values
- e. Median, and 1st and 3rd quartile values

For the PK parameters  $t_{max}$ ,  $t_{1/2}$ ,  $\lambda_z$ ,  $CL/F$ ,  $V_d/F$ , and  $K_a$  the following descriptive summary statistics will be reported on the untransformed scale:

- a. Count of subjects with non-missing data for the applicable analysis
- b. Arithmetic mean
- c. Standard deviation
- d. Minimum and maximum values
- e. Median, and 1st and 3rd quartile values

Bioavailability of SL administration of atropine sulfate relative to that of IM atropine sulfate will be assessed based on ratios of least-square means and their associated 90% confidence intervals (CIs) generated from linear mixed models to the log-transformed PK parameters including terms for dosing sequence, route (SL or IM), and period as fixed effects, and subject nested within dosing sequence as a random effect. No adjustment will be made for dosing cohort or the interaction for dosing cohort and route.

Ratios of least-squares means of key plasma PK parameters and associated 90% CIs from the linear mixed model will be anti-log transformed to obtain estimates on the original scale.

Bioequivalence will be considered met if the 90% CI of the ratio for  $AUC_{\infty}$  and  $AUC_t$  lie within 80.00 to 125.00%.

Subject specific and population time-concentration profiles on both log and linear scales will be presented. Additionally, PK parameters will be listed by route of administration and subject.

As a supportive analysis of bioavailability, descriptive summary statistics will be displayed in tables for subject-specific ratios between routes of administration.

For each PK parameter, boxplots will be displayed for each route of administration with subject specific lines overlaid.

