13.2. Sample Size Considerations

The target sample size for randomization for this study is approximately 46 participants, allowing for a 20% dropout rate that would result in approximately 36 evaluable participants (approximately 18 per dosing sequence) within the per protocol population. Additional participants may be randomized if participants are withdrawn prior to receiving one or both doses of study drug (Section 8.2.2).

The sample size was determined for an equivalence test of the ratio of means using two one-sided tests on data from a two-period cross-over design. In the previous PK study of SL administration of atropine (BP-C-19010),⁸ the standard deviation for the dose-adjusted log10 difference in high (1.0 mg) versus low (0.5 mg) SL dosing for AUC_{∞} and C_{max} were 0.102 and 0.146, respectively. Since the intra-participant variability in PK parameters between SL and IM administration is unknown, the standard deviations were conservatively multiplied by a factor of 1.25 to determine power and sample size for this study. Corresponding coefficients of variance were estimated as 0.212 and 0.304 for AUC_{∞} and C_{max} , respectively. A sample size of 36 achieves greater than 99% power to test bioequivalence for AUC_{∞} and 86% power for C_{max} at the 0.05 significance level when the true ratio of means is 1.0 and the equivalence limits are 0.80 and 1.25. Even if the true ratio of means are within $\pm 5\%$ of 1.0, the study still maintains 96% and 77% power for AUC_{∞} and C_{max} , respectively.

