#### 4. GENERAL ANALYSES AND REPORTING CONVENTIONS

The following is a list of general analysis and reporting conventions to be applied for this study:

- Validation and quality control of analysis datasets, tables, listings, and figures will be performed as specified in the Statistical Validation and Quality Control Plan (SVP).
- Categorical variables will be summarized using counts (n) and percentages (%) and will be presented in the form n (%). Percentages will be rounded to one decimal place. If n=0, then no percent will be shown. To ensure completeness, all summaries for categorical and discrete variables will include all reportable categories, even if none of the participants had a response in a particular category.
- Numeric variables will be summarized using n, mean, standard deviation (SD), median, minimum (min), and maximum (max). For variables summarized using geometric means, coefficient of variation (CV%) of the geometric mean will be presented in lieu of SD. The min/max will be reported at the same level of significance as original data. The mean and median will be reported at one more significant digit than the precision of the data. SD and confidence intervals (CIs) will be reported at two more significant digits than the precision of the data. Precision may be modified based on clinical judgement.
- The median will be reported as the average of the two middle numbers if the dataset contains an even number of observations.
- Test statistics including t and z test statistics will be reported to two decimal places.
- P-values will be reported to 3 decimal places if greater than or equal to 0.001. If less than 0.001, the value will be reported as “<0.001”.
- In general, listings will be displayed by dosing sequence and participant and will be sorted in the order that columns are displayed, starting with the first column on the left.
- All analyses will be performed using the SAS System version 9.4 or higher. Figures will be programmed using SAS version 9.4 or higher or R version 3.4.1 or higher.
- Dates will be displayed as ddmmmyyyy (e.g., 26May2023).
- Calculations using dates will be performed as noted below.

*Visit 1 Date = Day 1*

Study day for dates after Visit 1/Day 1

*Study Day = Date – Visit 1 Date + 1*

Study day for dates prior to Visit 1/Day 1

*Study Day = Date – Visit 1 Date*

Total duration of days

Page 16 of 35

$$\text{Duration} = \text{End Date} - \text{Start Date} + 1$$

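### Does the geometric CV% equation in SAP 11.2.2 put the −1 outside the square root, and does the plan need correcting for it?

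*SAP*

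**What the plan says.** SAP section 11.2.2 lists the summary statistics for the eight AUC parameters and Cmax. Item c is the "CV% of the geometric mean, which is calculated using the following equation". Under the root sign, the extracted equation continues "10^{\ln(10) \times (SD(\log_{10} value))^2}} - 1 \times 100". The brace that closes the root falls after the squared SD and before the minus sign.

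SAP section 4 sets the general convention: "For variables summarized using geometric means, coefficient of variation (CV%) of the geometric mean will be presented in lieu of SD". It gives no equation of its own, so 11.2.2 is the only place where the statistic is defined. The same table also shows the count, geometric mean, minimum, maximum, median and quartiles.

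**The concern.** For log-normal data the CV is the square root of (exp(σ²) − 1), with the −1 under the root. Here the −1 appears to stand outside, and nothing groups it before the multiplication by 100. Neither way of reading that string gives a CV.

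The row covers nine parameters, including both primary endpoints, and it replaces the SD for them. A programmer who followed the string would report a wrong measure of spread for all nine. Under the bracketed reading the values would be small but plausible, so the error might not stand out.

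**Working it through.** **Inputs.** Protocol section 13.2 gives SDs of the dose-adjusted log10 difference, for AUC to infinity and Cmax, that "were 0.102 and 0.146, respectively". It says that "the standard deviations were conservatively multiplied by a factor of 1.25". It then states the result: "Corresponding coefficients of variance were estimated as 0.212 and 0.304". The SAP equation has no worked value of its own, so these planning CVs are the nearest check on which form the sponsor uses.

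**Formula.** With s = SD(log10 value), σ = ln(10) × s, so exp(σ²) = 10^(ln(10) × s²). Call this v. The SAP's exponent is therefore right for log10 data, and the log-normal CV% is 100 × sqrt(v − 1).

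**Reproducing the protocol's CVs.** Within-subject s = SD of the difference × 1.25 / sqrt(2).

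- AUC to infinity: 0.102 × 1.25 / 1.4142 = 0.0902; v = 1.0440; sqrt(v − 1) = 0.210 (stated 0.212).
- Cmax: 0.146 × 1.25 / 1.4142 = 0.1290; v = 1.0923; sqrt(v − 1) = 0.304 (stated 0.304).

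The AUC figure is about 1% low. Rounding of 0.102 allows only 0.209 to 0.211, and an SD of 0.103 would give 0.212. The difference has no practical effect on power.

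**The alternative readings at the same SDs.**

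| Reading | AUC to infinity | Cmax |
|---|---|---|
| 100 × sqrt(v − 1) | 21.0% | 30.4% |
| (sqrt(v) − 1) × 100 | 2.2% | 4.5% |
| sqrt(v) − 1 × 100, strict order | −98.98 | −98.95 |

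Only the first row resembles the protocol's figures.

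**Size if the bracketed reading were programmed.** The table will use the across-subject SD within each route, which the documents do not give. Over an assumed range of true CV, with v = 1 + CV²:

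| True CV | Bracketed reading | Understated by a factor of |
|---|---|---|
| 20% | 2.0% | 10.1 |
| 30% | 4.4% | 6.8 |
| 40% | 7.7% | 5.2 |
| 50% | 11.8% | 4.2 |
| 60% | 16.6% | 3.6 |

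**Would the table show it?** At a true CV of 30.4%, σ = 0.2971. The ratio of upper to lower quartile is exp(2 × 0.6745 × 0.2971) = 1.49. A reported CV of 4.5% would imply σ = 0.0451 and a quartile ratio of exp(2 × 0.6745 × 0.0451) = 1.06. The quartiles printed in the same table would contradict the CV.

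**What depends on the equation.** SAP section 11.2.2 bases bioequivalence on the 90% confidence interval of the ratio from the mixed model on log-transformed parameters, which does not use the CV% row. The power in protocol section 13.2 rests on the CVs reproduced above. "A sample size of 36 achieves greater than 99% power to test bioequivalence" for AUC to infinity, and recalculation with two one-sided tests (36 participants, 34 degrees of freedom) gives 99.5%. For Cmax it gives 86.0% against a stated 86%.

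**The case for a change.** The best argument for a correction is that the SAP is the binding text. Section 2 gives it primacy over the protocol, section 4 lets the specific section override the general conventions, and no second equation exists. A programmer who follows the string gets a wrong value, while one who silently repairs it departs from an approved formula. A validator working from the same text could repeat the error. A CV of 4% or 12% would not look absurd on its own.

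It is true that the extracted string does not define a CV and that nothing else in the SAP supplies the formula. The rest is weaker. To reach the bracketed reading, a programmer would have to add brackets that are not printed and arrive at a non-standard statistic. Strict order gives about −99, which no one would release as a CV. The correct formula needs no brackets, and shortening its root bar yields exactly the string seen. An author who has the less obvious log10 exponent right and includes a −1 is writing the standard geometric CV. Section 6 of the SAP also puts tables and analyses through validation and quality control.

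**Conclusion.** No change to the plan. The intended statistic is clear: 100 × sqrt(10^(ln(10) × s²) − 1), with s the SD of the log10 values. The departure is either a clerical slip in the root bar or an effect of extracting the equation from the PDF. The extracted text cannot show which, but a glance at the printed equation will, and the answer is the same in both cases. An analyst would program the usual geometric CV.

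If the string were nevertheless programmed in its bracketed reading, one descriptive row for nine parameters would be understated, by a factor of about 10 at a true CV of 20% and 3.6 at 60%. Those CVs are assumed, since the across-subject SDs are not given. The bioequivalence conclusion would not move.
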